**PROPOSED DEPARTMENT & PLACE OF STUDY:**

Dept. of Orthodontics, Faculty of Dentistry, Jamia Millia Islamia, New Delhi

**OBJECTIVES:**

1. To assess oral health related quality of life in patients undergoing canine disimpaction through Questionnaire.
2. To assess periodontal outcomes between the open and closed surgical techniques.
3. To assess whether there are differences in patient reported outcomes between the open and closed surgical techniques.

**1. BACKGROUND KNOWLEDGE:**

Impacted canines are permanent teeth that could not erupt at its normal chronological age due to its displacement to abnormal position in the roof of mouth (palate), or due to obstruction in its path of eruption or inherent deficient eruption potential. This is a frequently occurring anomaly, present in 2% to 3% of the population. Management of this problem is both time consuming and expensive and involves surgical exposure (uncovering of palatal mucosa) along with fixed orthodontic appliance to bring the canine into its normal position and alignment within the dental arch.

Two techniques for surgical exposure of palatally impacted canines are routinely followed:

- a) **Open surgical technique**, involves surgical uncovering of the palatal mucosa overlying impacted canine by creation of a window in the palatal mucosa, and a dressing is placed to cover the exposed area. Then approximately 10 days later, this pack is removed and the canine is allowed to erupt naturally. Once the tooth has erupted sufficiently for an orthodontic attachment to be bonded to its surface, orthodontic treatment is commenced to bring this tooth into its correct position in dental arch the through the palatal mucosa.
- b) **Closed surgical technique** involves surgical uncovering of palatal mucosa above the impacted canine by full thickness flap and bonding an attachment over the exposed

surface of canine, repositioning/suturing of palatal mucosa and then with the help of bonded attachment, orthodontically moving this canine into its correct position from beneath the palatal mucosa.

## 2. REASON OF THE STUDY:

Through this prospective study, clinical outcomes and patient experiences for both these techniques will be evaluated.

Permanent maxillary canines usually erupt in the mouth at the age of 11 to 12 years. They play a vital role in facial appearance, dental aesthetics, arch development and functional occlusion i.e the canine guided occlusion. The process of eruption of the permanent canines leading to their final positioning in the oral cavity is complex and the longest of all the permanent teeth which may leads to impaction or eruption of these canines into abnormal position. Impacted canines are usually asymptomatic, however, impaction may cause severe complications such as development of malocclusion and some pathological conditions e.g. dentigerous cysts. The most common irreversible and adverse effect of maxillary canine impaction is root resorptions. Their impaction can also cause damage to the roots of neighboring teeth by causing resorption of their roots and the damage may be so severe that these teeth are subsequently lost. The tissue that is the dental follicle around these impacted canine teeth may undergo cystic changes. Impaction of these teeth can also lead to aesthetic problems due to a gap created in the dental arch in the area at their position. Hence negative physical and psychological impact can occur to the patient. Therefore it is important to disimpact these teeth and bring them into their correct occlusal position within the dental arch.

There are only a few clinical trials, where open and closed surgical exposure of canine are compared on various outcomes. Most of these studies are retrospective and due to the biases involved, they provide very little conclusive evidence.

A study by Wisth compared closed and open techniques. 34 participants received an open exposure and 22 patients received a closed exposure. It was found that the mean duration of treatment was 4 months longer in the closed group and it was reported that this was likely due to lack of direct vision of the canine from when it was exposed to when it was brought into the line of the arch. The closed group appeared to have less periodontal damage in terms of loss of attachment and bone levels. The study however was retrospective, pretreatment equivalence was not established (in terms of participant's

age or severity of canine displacement) and therefore the risk of selection and detection bias was high.

Woloshyn study, all palatally displaced canines received a closed exposure. This study found that the roots of the impacted canine and adjacent lateral incisor were slightly shorter than those of the contralateral canine and that the treated canine could be visually differentiated from the control canine in 70% to 80% of cases. They came to a conclusion that the overall consequences to the impacted canine with open technique seem better than with a closed technique. This is in contrast to findings of Becker reported excellent periodontal health following alignment of canines using a closed technique. Importantly, all these mentioned studies, are retrospective and findings therefore score low in terms of evidence.

Sampaziotis et al in their systematic review concluded that there is a need for randomized clinical trials (RCTs) to compare the two treatment alternatives and more RCTs should be performed in the future for stronger evidence and clarification of some controversial issues.

According to a recent Cochrane review, the studies conducted had high risk of bias and thus were very low in evidence to support any decision. Thus, particular conclusion as to which technique of surgical exposure is superior in terms of periodontal health, aesthetic and patient comfort cannot be attained.

The present study has been designed keeping the lacunae in previous literature in mind. Currently, there is little evidence to support one surgical technique over the other in terms of dental health, aesthetics and patient factors. Therefore, a high quality prospective clinical trial with participants randomly allocated into the two treatment groups need to be conducted. Otherwise, methods of exposing canines will be left to the personal choice of the surgeon and orthodontist.

### 3. METHODOLOGY:

**Study design:** A unicentric, randomized controlled clinical trial involving 2 parallel groups (Group 1 for open surgical technique and group 2 for closed surgical technique) where contralateral side fully erupted and normally positioned canine will be considered as control. The study will be conducted in Department of Orthodontics, Faculty of

Dentistry, Jamia Millia Islamia post ethical committee approval by institutional ethics committee.

Written informed consent will be taken from all the patients enrolling in the study.

Estimation of Sample Size: Assuming the mean difference of the primary outcome (measure of clinical attachment) as 0.5 mm with standard deviation as 0.61 mm between the open and closed exposure group (Reference : Periodontal health of palatally displaced canines treated with open or closed surgical technique: A multicenter, randomized controlled trial. American Journal of Orthodontics and Dentofacial Orthopedics August 2013 ; 176-84; Vol 144 ;Issue 2) with alpha (level of significance) <0.05 , Power=80% , 2 sided hypothesis, the total minimum sample size 40 will be required to detect the minimum significant difference of the primary outcome. The total sample size can be randomized in equal no. as 20 in each group (open and closed group). Twenty patients who meet the below mentioned criteria will be randomly allocated in each group. Participants for the trial will be identified from treatment waiting lists and new patient clinics.

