### **Inclusion criteria:**

- Patients with unilateral and favorably placed palatally ectopic maxillary canines who require surgical exposure for orthodontic alignment of impacted canine on contralateral side of same arch. The other side will be taken as control canine.
- Age 13-25 years
- Minimal orthodontic malocclusion other than the ectopic canine
- Good oral hygiene and motivation to wear fixed appliances for at least 2 years

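### Forty patients do not give 80% power for a two-sided 5% test under the protocol's own inputs: 20 per arm gives about 71%, and 40 is the number a one-sided 5% t-test would need

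*Protocol*

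**What the plan says.** The whole calculation stands in one paragraph of the protocol, section 3 (Methodology), under the estimation of sample size. The effect and variability are given as: "Assuming the mean difference of the primary outcome (measure of clinical attachment) as 0.5 mm with standard deviation as 0.61 mm". The significance level is entered "with alpha (level of significance) <0.05", and the conclusion reads: "Power=80% , 2 sided hypothesis, the total minimum sample size 40 will be required to detect the minimum significant difference of the primary outcome". The allocation follows: "The total sample size can be randomized in equal no. as 20 in each group (open and closed group". The same section describes a randomised trial with two parallel groups.

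The paragraph mentions no dropout allowance, covariate adjustment or other design factor. On follow-up, the inclusion criteria ask for "Good oral hygiene and motivation to wear fixed appliances for at least 2 years", and Annexure 2 places the periodontal measurements one month after debonding.

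**The concern.** A difference of 0.5 mm against an SD of 0.61 mm is a standardised effect of about 0.82. Twenty per arm is too few to detect that with 80% power in a two-sided 5% test, so sidedness, power and total cannot all be right together.

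The trial sets out to show which exposure technique should be used, and it criticises earlier work as weak evidence. Anyone weighing a non-significant result against a claimed 80% power would give it more weight than the design supports. Because 40 is called the minimum and exactly 40 are to be randomised, any patient lost before the post-debond measurement lowers power further.

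**Working it through.** **Inputs**, all from the sample-size paragraph: difference 0.5 mm; SD 0.61 mm, read as the common within-group SD; alpha 0.05, two-sided; power 80%; two independent groups, 1:1; stated result 20 per arm, 40 in total.

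**Standardised effect.** d = 0.5 / 0.61 = 0.8197.

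**Step 1: try to reproduce 40 as stated (two-sided 5%, 80% power).**

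- Normal approximation: n per arm = 2 × (1.960 + 0.8416)² / 0.8197² = 23.36, so 24 per arm, 48 in total.
- t-test (noncentral t): n per arm = 24.36, so 25 per arm, 50 in total, with power 81.0%.

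Neither gives 40. The shortfall is 8 patients by the first method and 10 by the second.

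**Step 2: power at the stated 20 per arm, two-sided.**

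- Noncentrality: 0.5 / (0.61 × √(2/20)) = 2.592.
- Normal approximation: Φ(2.592 − 1.960) = 73.6%.
- t-test with 38 degrees of freedom: 71.4%.

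The type II error by the t-test is 100% − 71.4% = 28.6%, against the 20% implied.

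**Step 3: what 20 per arm can do with 80% two-sided power (t-test).**

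- Keeping SD 0.61 mm, the detectable difference is 0.555 mm (0.540 mm by the normal approximation).
- Keeping 0.5 mm, the SD would have to be 0.55 mm (0.56 mm by the normal approximation).

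**Step 4: readings that might give 40.**

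| Reading | n | Total | Gives 40? |
|---|---|---|---|
| One-sided 5%, t-test | 19.12, so 20 per arm (power 81.6%; 19 per arm gives 79.8%) | 40 | Yes |
| One-sided 5%, normal approximation | 18.40, so 19 per arm | 38 | Nearly |
| 0.61 as the SD of a difference between two patients (0.61/√2 = 0.431 per arm), two-sided, normal | 12 per arm | 24 | No |
| 0.61 as the SD of a paired difference, two-sided | 12 pairs (normal); 13.73, so 14 pairs (t) | 12 or 14 | No |

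Of these readings, only the one-sided 5% t-test gives exactly 40. For sample size it is equivalent to a two-sided 10% test. Either contradicts the stated "2 sided hypothesis" at 5%.

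**Step 5: effect of loss.** The protocol gives no loss rate, so these rates are assumptions for illustration. Two-sided t-test, difference 0.5 mm, SD 0.61 mm:

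| Assumed loss | Evaluable per arm | Power |
|---|---|---|
| 0% | 20 | 71.4% |
| 10% | 18 | 66.6% |
| 15% | 17 | 64.0% |
| 20% | 16 | 61.2% |

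**The case against.** The strongest defence is that 71% is the power of an unadjusted two-sample comparison. The SD is worded loosely ("with standard deviation as 0.61 mm between the open and closed exposure group"), and each patient's contralateral canine is named as a control. If the analysis used that tooth as a covariate and the correlation were about 0.45, power at 20 per arm would be about 81% (about 79% at a correlation of 0.40). But the protocol states neither an adjustment nor a correlation, so this cannot justify its figure. What stands is that the corrected sentence should name the analysis to which the power refers.

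Three qualifications also stand:

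- **Cause.** That a one-sided calculation was run is inferred from the numerical match. An SD of about 0.55 mm would also fit. The inconsistency does not depend on the cause.
- **Loss.** The loss rates are assumed, and the two-year figure is an eligibility criterion about motivation rather than a fixed treatment duration. The shortfall exists at zero loss.
- **Outcome.** The calculation is for clinical attachment, whereas the primary outcomes listed later are quality of life and width of attached gingiva. This is a separate problem; correcting the arithmetic does not solve it.

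It can also be said that nine points of power is a modest shortfall and that the protocol claims no equivalence. That bears on how much harm follows, not on whether the statement is right. A separate statistical analysis plan would not cure it either, because the protocol gives the calculation in full and its result is wrong.

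**Conclusion.** The concern holds. The stated two-sided 5% test, 80% power and total of 40 are mutually inconsistent for a 0.5 mm difference with SD 0.61 mm. Forty patients give 71.4% power, about 9 points below the claim, and 80% power would need 48 to 50 patients before any loss. This rests on an unadjusted comparison of two independent groups and on 0.61 mm being the within-group SD. The other readings of that SD tried above do not give 40. The source trial cited for the inputs was not examined; the finding concerns only whether the protocol's result follows from its own inputs.

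**What to change.** Rewrite the sample-size paragraph so that the two-sided test, 80% power and 40 patients no longer appear together. Either:

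- **Keep 40 patients.** State that 20 per arm gives about 71% power to detect 0.5 mm (SD 0.61 mm, two-sided 5%, unadjusted t-test), or 80% power to detect about 0.55 mm. Add the power at the number expected to be evaluable one month after debonding, with the assumed loss rate stated. If a covariate-adjusted analysis is intended, name it and give the assumed correlation.
- **Keep 0.5 mm at 80% power.** State that 25 per arm are needed before loss. With assumed losses of 10%, 15% or 20% this becomes 25/0.90, 25/0.85 or 25/0.80, that is 28, 30 or 32 per arm.

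The first option costs one corrected paragraph and a less favourable stated power, with no extra patients. The second costs at least 10 more patients.

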### **Inclusion criteria:**

- Patients with unilateral and favorably placed palatally ectopic maxillary canines who require surgical exposure for orthodontic alignment of impacted canine on contralateral side of same arch. The other side will be taken as control canine.
- Age 13-25 years
- Minimal orthodontic malocclusion other than the ectopic canine
- Good oral hygiene and motivation to wear fixed appliances for at least 2 years

### **Exclusion criteria:**

- Patients with contralateral ectopic maxillary canines.
- Periodontal disease (bleeding on probing, pocket probing depths 3 mm and decreased bone levels as diagnosed from baseline panoramic imaging)
- Cases in which the canine is to be brought into the position of the lateral incisor or premolar.
- Compromising medical conditions (patients requiring antibiotic prophylaxis to prevent infective endocarditis)

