#### **2. Allocation concealment and implementation of the random allocation sequence:**

Blinding of the investigator is not possible so to reduce bias one of the staff assistant who was neutral towards treatment will be allocated the job of assigning patient in the two treatment groups. The first 5 patients will be allocated according to simple randomization and from 6th patient onwards minimization will be followed.

The prognostic factors or predictors will be used like severity of impaction, age, oral hygiene, presence of crowding, and rotation of canine. The severity of the canine impaction will be assessed by a single blinded assessor, from the pretreatment panoramic imaging film, using the criteria described by Ericson and Kurol.

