**2. CLINICAL OUTCOMES (Annexure 2)**  
 (To be measured after 1 month post debond):

Group: open/closed	
1. Pocket Depth	
2. KT width	
3. 
 
a. Gingival recession, if any, measured on the buccal midpoint of the canine crown.
 
b. Gingival recession, if any, measured on the buccal midpoint of the L.I. crown.
 
	
4. Clinical crown length-incisal edge to gingival margin on midfacial surface parallel to the long axis.	
5. Clinical crown length-incisal edge to gingival margin on midfacial surface parallel to the long axis of the contralateral tooth	
6. Time period it took to align	DOE DOA
7. How many times did bracket debond	
8. How many times flap was raised.	
9. Probing bone level-subtracting the distance CEJ to gingival margin from the distance gingival margin to bone.	
10. Bleeding on probing	
11. Loe and silness score	

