## Baseline Data

Patient's name:

Age/sex:

UID no:

Case no:

Contact number:

Address:

Side of Impaction

Severity of Impaction (Ericson and Kurol)

Angle:

Vertical height:

Sector:

Oral Hygiene:

Date of start of fixed treatment:

Date of surgical exposure:

Date of alignment of canine:

Date of debonding:

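### The baseline sheet has no fields for periodontal readings at erupted teeth, so existing lateral-incisor recession and periodontal status cannot be separated from change during treatment

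*Protocol*

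**What the plan says.** The Exclusion criteria rule out periodontal disease and list its signs in brackets: "bleeding on probing, pocket probing depths 3 mm and decreased bone levels as diagnosed from baseline panoramic imaging". Two of the three signs are probing findings. The Inclusion criteria ask for "Good oral hygiene and motivation to wear fixed appliances for at least 2 years", with no index or cut-off. The section on allocation concealment gives the minimization factors as "severity of impaction, age, oral hygiene, presence of crowding, and rotation of canine".

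Periodontal results go on the Annexure 2 sheet, headed "To be measured after 1 month post debond". It covers pocket depth (item 1), recession on the canine and the lateral incisor (items 3a and 3b), bleeding (item 10) and the Loe and Silness score (item 11). The Primary Outcome Measures section cites this sheet and names recession among its periodontal measures. It does not name pocket depth or bleeding.

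The Baseline Data sheet has fields for the angle, vertical height and sector of the impaction and a single line for oral hygiene. It has none for probing depth, bleeding, the Loe and Silness score or recession of any tooth. Quality of life is handled differently: Annexure 1 has both a pre-treatment and a post-treatment OHIP-14 form.

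**The concern.** A periodontal reading taken only after treatment mixes what the patient brought to the trial with what happened during it. For the impacted canine this is unavoidable. For the lateral incisor, and for the general state of the gums, it is not, because those teeth can be examined before treatment starts.

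Two things are at stake. First, item 3b cannot show whether recession on the lateral incisor is new. Second, with 20 patients per arm, differences between patients in starting periodontal state remain in the residual variance, and a chance imbalance between arms could be neither described nor adjusted for. A statistical analysis plan can choose a model, but it cannot use readings that the forms never captured.

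**Working it through.** **1. The forms side by side.**

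| Reading | Baseline Data sheet | Annexure 2, after debond | Readable before treatment? |
|---|---|---|---|
| Pocket depth | no field | item 1 (tooth not stated) | at erupted teeth |
| Bleeding on probing | no field | item 10 (tooth not stated) | at erupted teeth |
| Loe and Silness score | no field; one free oral hygiene line | item 11 (tooth not stated) | at erupted teeth |
| Lateral-incisor recession | no field | item 3b | yes, on the same tooth (assumed erupted) |
| Canine recession | no field | item 3a | no, the tooth is impacted |
| Contralateral (control) canine | no field | crown length only (item 5) | yes |

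Item 3b is the clearest loss: same tooth, same measure, readable at both times, recorded at one. The control canine does not fill the gap, since the only Annexure 2 item expressly assigned to it is crown length.

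**2. How scarce precision is.** The sample-size paragraph under Methodology assumes a difference "as 0.5 mm with standard deviation as 0.61 mm between the open and closed exposure group", with "alpha (level of significance) <0.05 , Power=80% , 2 sided hypothesis", and gives 40 in total. The usual two-sided formula gives

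n per arm = 2 × (0.61 × (1.960 + 0.842) / 0.5)² = 23.4, so 24 per arm, 48 in total.

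The t-based calculation gives 24.4, so 25 per arm, 50 in total. The stated 40 is not reproduced. At 20 per arm the standard error is 0.61 × √(2/20) = 0.193 mm. Then 0.5/0.193 − 1.960 = 0.63, a power of 73.6% (71.4% with the t distribution). That is a separate matter. It matters here only because it leaves no spare precision.

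**3. What a starting value could do for item 3b.** Let r be the correlation between starting and final lateral-incisor recession. Adjustment multiplies the residual variance by 1 − r². Estimating one slope costs on average a factor of 1 + 1/(40 − 4) = 37/36 = 1.028, for a roughly normal covariate. The two balance at r² = 1/37, so r is about 0.16. The documents give no r. Purely as an illustration, for this item alone:

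- r = 0.3: 0.91 × 1.028 = 0.94
- r = 0.6: 0.64 × 1.028 = 0.66

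Recession is recorded only if present. If most values are zero, r could be lower.

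**4. The canine items.** No starting value exists on the impacted tooth. A covariate would have to come from other teeth or from a patient-level score, and the documents offer nothing on how strongly these relate to the final canine reading. No figure can be given.

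**The case against.** The strongest case against the point has four parts.

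- *Starting status is already controlled.* Good oral hygiene is required for entry, oral hygiene is a minimization factor, and allocation is random. This stands in large part: what remains is added variance and residual chance imbalance, not systematic bias between techniques. It does not remove the gap, because oral hygiene has no stated index and probing depth, bleeding and bone level are not minimization factors.
- *Adjustment belongs in the statistical analysis plan.* True of the model, and its absence here is no finding. The form fields are a matter for this protocol.
- *The readings may be kept in the clinical record.* Possible. The protocol does not say that screening findings are discarded, only the trial's own sheet has no place for them.
- *The tooth of interest cannot be probed at baseline.* Correct. This limits the point to item 3b and to patient-level status.

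A reader might also infer from the word *and* in the exclusion that patients with bleeding pockets but normal bone are admitted. The documents do not establish this. The criterion excludes periodontal disease, and the bracket can be read either as a list of its signs or as a set of joint conditions, since neither *any* nor *all* is stated. That is an ambiguity to clear up, not a proven admission of diseased patients. The text shown also has no comparator in "pocket probing depths 3 mm". A symbol may have been lost in reading the file, so nothing is made of that.

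**Conclusion.** The point holds as a cheap improvement. Pre-treatment status at erupted teeth has no place on the baseline sheet, while the matching items are collected once, 1 month after debond. The consequence is certain for item 3b, where existing recession cannot be separated from new recession. For patient-level status it is a possible loss of precision of unknown size.

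A reader might go further and put figures on the main comparison. Taking r = 0.3 to 0.6, 20/(1 − r²) gives about 22 to 31 effective patients per arm. Two extra patients with pockets 2 mm deeper in one arm would shift its mean by 2 × 2/20 = 0.2 mm, or 40% of 0.5 mm. Neither figure is supported:

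- Both need a baseline reading that the impacted canine cannot give, and a correlation between teeth that the documents do not supply.
- The 0.5 mm refers to clinical attachment, not to pocket depth at other teeth.
- The 0.2 mm assumes that a starting difference carries over in full. With the same r and equal standard deviations it would be 0.06 to 0.12 mm, or 12% to 24% of 0.5 mm, and even that needs the link between teeth.

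The verdict rests on the sheets as shown and on the lateral incisor being erupted and measurable at entry.

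**What to change.** 1. Add to the Baseline Data sheet, recorded before allocation: probing depth, bleeding on probing and the Loe and Silness score at named erupted teeth, and recession of the lateral incisor. Recession of the contralateral canine is optional.
2. Analyse item 3b adjusted for its baseline value. Use the bleeding and Loe and Silness readings as patient-level covariates where useful, chosen before the data are seen.
3. Separately, have the sponsor state whether any one or all of the signs listed in the periodontal exclusion rule a patient out. No rule is proposed here, as the choice affects recruitment in a way the documents do not allow one to estimate.

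The cost is a few more readings and one covariate in the model. If all three signs are needed to exclude, a normal film alone could settle eligibility and probing might be skipped. The readings would then need a short examination of their own. Readings not taken before treatment cannot be recovered later.
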